# 1.2. Effect of Intermittent Fasting on Metabolic Parameters

In contrast to the DASH diet, intermittent fasting (IF) is a dietary pattern that emphasizes temporal restriction of caloric intake rather than restricting the number of calories and/or changing the types of foods eaten. The simplest and most popular variation of IF involves restricting caloric intake to an 8-hour period each day, and consuming no calories for the other 16 hours (so-called 16:8 time-restricted feeding). In animal studies, IF has been shown to activate cellular pathways with potential disease-modifying benefits in a number of conditions. In small human studies, IF is associated with a reduction in SBP by 5-10 mmHg, LDL cholesterol by ~8 mg/dl, and weight by ~ 3 kg, though none of the studies of a time-restricted feeding regimen included concurrent controls. Some patients report that IF is easier to initiate and maintain than other dietary patterns, though this has not been tested empirically.

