#### 5. Statistical Methods

# 5.1 Primary and secondary outcome measures

The study's primary outcome measure is adherence to the IF regimen, captured via daily text message, over 18 weeks, expressed in days per week.

Secondary outcome measures will include:

- 1) Adherence to the IF regimen over 12 weeks
- 2) Change in systolic blood pressure from baseline to 12 weeks and 18 weeks
- 3) Change in weight from baseline to 12 weeks and 18 weeks

Exploratory analyses will compare change in blood pressure and weight in patients that were adherent to IF  $\geq$  4 days per week vs.  $\leq$  4 days per week

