#### 5.3. Data Analyses

Data for all patients who received at least 1 text message asking if they fasted the day prior, whether or not they completed all protocol requirements, will be included for analysis. Patient demographics, risk profiles, clinical characteristics, and baseline questionnaire results will be reported. All analyses will be performed using a modified intention-to-treat, excluding only patients who did not receive at least 1 text message asking if they fasted the day prior. Data can be missing for any day if the participant did not report adherence with daily fasting. For the main analysis, we will assume that days for which patients did not report adherence with daily fasting were non-adherent days. The primary analysis will compare days fasted per week between attention control and commitment device arms using a t test. Secondary analyses compare change from baseline in blood pressure and weight between arms using mixed effects regression models. Exploratory analyses will compare change from baseline in blood pressure and weight in patients who reported fasting  $\geq 4$  days/week versus those who reported fasting  $\leq 4$  days/week using mixed effects regression models.

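### The exploratory adherence-response analysis of blood pressure and weight splits daily fasting data at 4 days/week, with overlapping groups, no exposure window and no stated arm term

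*Combined protocol and SAP*

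**What the plan says.** Section 5.1 lists the comparison as "Exploratory analyses will compare change in blood pressure and weight in patients that were adherent to IF" on 4 or more days per week against 4 or fewer. Section 5.3 repeats it as "Exploratory analyses will compare change from baseline in blood pressure and weight in patients who reported fasting" at those two levels ("days/week versus those who reported fasting" joins the two groups, with the same two inequality signs) and adds that mixed effects regression will be used. Neither section names the weeks over which days/week is averaged, the outcome time for this comparison, or any covariate.

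The surrounding definitions offer two windows and two outcome times:

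- The primary outcome is "adherence to the IF regimen, captured via daily text message, over 18 weeks, expressed in days per week".
- The first secondary outcome is "Adherence to the IF regimen over 12 weeks".
- Blood pressure is assessed as "Change in systolic blood pressure from baseline to 12 weeks and 18 weeks", and weight at the same two times.

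Section 3.1 has adherence reported daily and weight and blood pressure weekly, for every patient. Under section 4.4.1 (Soft commitment device), the extra reminders and partner updates stop after week 12 in that arm. The daily adherence text runs for 18 weeks in that section, but for 16 weeks under section 4.4.1 (Attention control).

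**The concern.** Both arms are told to fast, so the randomised comparison of blood pressure and weight reflects whatever difference in adherence the commitment device produces. The comparison by adherence level is the only planned analysis that relates fasting itself to these outcomes. Readers will look to it for that, so it should use the data well and be defined before the data are seen.

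As written it leaves four gaps:

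- A day-by-day record becomes one label per patient, and variation on either side of the cut is lost.
- With no window, an 18-week average could classify a 12-week change. Fasting after week 12 cannot have caused that change, whereas a good reading at week 12 may encourage later fasting.
- Arm affects fasting by design and also brings a pledge and partner contact. Without an arm term, the two are mixed.
- A patient averaging exactly 4 days/week belongs to both groups.

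At stake are the precision and interpretability of an exploratory estimate, and a choice of window that could be made after seeing the results.

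**Working it through.** **The plan's own figure.** Section 5.2 gives no power for the adherence-level comparison. Its nearest figure is about 50% power for a 10 mmHg difference with SD 15 and 17 per arm. Two-sided alpha 0.05 is assumed, since none is stated. SE = 15 × √(2/17) = 5.145; 10/5.145 = 1.944; power = Φ(1.944 − 1.960) = 49%, or 47% with the t distribution. The figure reproduces for two groups of 17. Adherence groups need not be equal: by the t calculation the same effect has 40.5% power at 10 versus 24 and 33% at 7 versus 27.

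**Information kept by a two-group split.** The documents give no adherence distribution, so it is an assumption here. For a normal exposure and a linear response, the share kept is φ(z)²/[p(1 − p)], where p is the proportion on one side of the cut and z the matching normal quantile.

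| Split | Share kept | Lost | Equivalent N of 34 |
|---|---|---|---|
| 50:50 | 0.637 | 36% | 21.6 |
| 70:30 | 0.576 | 42% | 19.6 |
| 80:20 | 0.490 | 51% | 16.7 |

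To illustrate, suppose a true correlation of 0.4 between exposure and change. Power by Fisher's z is Φ(atanh(r) × √31 − 1.96). That is 65.5% for the continuous exposure. With r multiplied by the square root of the share kept, it is 45%, 41.5% and 36% for the three splits.

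Other shapes lose less. For a uniform exposure on 0 to 7 cut at 4, the group means are 5.5 and 2 with proportions 3/7 and 4/7. The share kept is (3/7)(4/7)(3.5²)/(49/12) = 3.00/4.08 = 73%. A U-shaped Beta(0.5, 0.5) exposure scaled to 0 to 7 keeps 80%. Two well-separated clusters centred at 1 and 5.5 keep about 91%.

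**What an unmatched window could do.** Weeks 13 to 18 are 6/18 = 33% of an 18-week mean. With A the mean over weeks 1 to 12 and B the mean over weeks 13 to 18, the 18-week mean is (12A + 6B)/18, which equals 4 when B = 12 − 2A.

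- A = 5: the patient falls below 4 if B is under 2.
- A = 4.5: the patient falls below 4 if B is under 3.
- A = 3.5: the patient reaches 4 if B is at least 5.

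In simulation with assumed mean 4 to 5, SD 1.24 to 2.0, between-period correlation 0.5 to 0.8 and a drop of 0 to 2 days after week 12, 5% to 24% of patients changed group. That is about 2 to 8 of 34. It measures reclassification, not bias.

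**Texting period.** If control texts stop at 16 weeks and unreported days count as non-adherent, a control patient needs 4 × 18/16 = 4.5 days/week over 16 weeks to average 4 over 18. Section 5.3 states the missing-day rule for the main analysis only. Whether it applies here is not said.

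**Which continuous exposure.** Cumulative days fasted rise mechanically with time. At an assumed mean of 4.5 and SD 1.24 days/week, their correlation with study week is 0.87. In a simulation of 60 trials with no fasting effect and an assumed common fall of 6 mmHg over 18 weeks, a model of weekly readings on cumulative days without a week term was significant in 100%. Adding study week brought this to 5%. Using mean days/week to date gave 3%.

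**The case against.** The strongest reply is that the plan does not contain the mismatch. A reader might infer that the 18-week primary measure will classify the 12-week change. But section 5.1 also defines 12-week adherence, directly above outcomes at 12 and 18 weeks, and matching like with like is at least as natural a reading. That stands: the text permits the mismatch and does not plan it.

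A reader might also infer that the estimate will be inflated by reverse causation. The documents give no basis for a size, and classification by irrelevant later weeks could equally dilute the contrast. That stands too.

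The comparison is labelled exploratory, and objective 2 in section 2 concerns the effect of the intervention promoting fasting, which the randomised comparison addresses. Section 1.2 says of earlier work, "though none of the studies of a time-restricted feeding regimen included concurrent controls". It would be wrong to present the adherence comparison as filling that gap, because its groups are not randomised.

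Finally, the normal model is only one scenario. Days/week is bounded, and counting unreported days as non-adherent may create a cluster near zero, where a split costs much less. This limits the size of the loss, but every shape examined shows some loss. Nothing in the objection supplies a window, an arm term or non-overlapping groups.

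**Conclusion.** The concern holds as a modest improvement to an exploratory analysis. The missing window, the unstated arm adjustment and the overlap at exactly 4 days/week are plain on the text.

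The cost of the split is 36% or more of the exposure information if mean days/week is roughly normal and the response linear. It is 9% to 27% under the uniform, U-shaped and two-cluster shapes tried. The documents do not show which applies. Use of weeks 13 to 18 for a 12-week change is possible under the wording but not specified, and no bias from it can be quantified. The primary adherence analysis and the randomised comparisons of blood pressure and weight are unaffected.

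**What to change.** In section 5.3, make continuous mean days/week the main exposure: over weeks 1 to 12 for the 12-week change and weeks 1 to 18 for the 18-week change, or mean days/week to date for each weekly reading. Fit it in the mixed model already planned, with terms for study week, arm and baseline value. Do not use raw cumulative days without a week term, because that would pick up any common trend over time.

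Keep any two-group display supplementary, with the same matched windows and with exactly 4 days/week assigned to one group only. State whether the missing-day rule applies to this exposure. Report the result as an exploratory association, since confounding and reverse causation within the window remain. Reconcile the 16-week and 18-week texting periods in the two parts of section 4.4.1 before any 18-week exposure is computed.

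The cost is SAP wording and a few model terms, with no new data. A slope per fasting day is less simple to present than two groups and assumes rough linearity.

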# 3. Study Design

#### 3.1. General Overview

The IFAST study is a two-arm randomized controlled trial aimed at evaluating whether a soft commitment device increases uptake and adherence to an intermittent fasting dietary pattern compared with control in patients with hypertension and obesity. The study will randomize 34 patients with hypertension and obesity to a 12-week intervention employing a commitment pledge, involvement of a supportive partner, setting of implementation intentions, and multiple daily reminder text messages or to an attention control involving daily text messages alone.

Following the intervention, there will be a 6-week follow-up period (see study protocol figure below).

The study will be conducted using Way to Health, a research information technology platform at the University of Pennsylvania used previously for behavioral interventions.

After institutional review board (IRB) approval of the study, patients who meet the eligibility criteria will be approached in select cardiology clinics and invited to participate. Those who qualify and express interest will provide informed consent to the study procedures via the Way to Health platform. All patients will receive a blood pressure cuff and scale, which will be used to measure blood pressure and weight weekly. Within the Way to Health platform, patients will be randomized to the intervention or control arms. All other management decisions are completely at the discretion of the care providers. Data capture will include:

- **Baseline case report form** (for each patient) collecting clinical information abstracted from the medical record
- **Baseline survey** collected via the Way to Health platform including psychometric questions, dietary patterns, and experiences with weight loss and dieting
- Daily adherence to an intermittent fasting dietary pattern collected via self-report from text messages
- Weekly weight and blood pressure measurement collected via self-report from text messages

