#### 4.4. Study Arms

#### 4.4.1 Attention control

These patients will be instructed via text message and email to fast at least 16 hours per day every day. For the next 16 weeks, they will receive a daily text message via the Way to Health

platform asking if they fasted for at least 16 hours over the past 24 hours. If they fail to respond, reminder text messages will be sent. Once per week, they will receive a text message asking them to weigh themselves and check their blood pressure, and reply with the results via text message

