#### 4.4.1. Soft commitment device

Patients randomized to the commitment device arm will be asked to visit the Way to Health platform. There, they will identify a support person, a family or friend who they speak to frequently and who is invested in their health. They will then complete a series of questions intended to create implementation intentions. Specifically, they will pick a time for their fast to begin each 24-hour period and a time for their fast to end. They will also develop strategies to deal with hunger arising during a fast period. After this process, they will sign a contract pledging to adhere to the 16:8 time-restricted feeding dietary pattern, and acknowledging that their support person will receive a copy of the contract and weekly updates about their adherence to the regimen.

For the next 12 weeks, participants in this arm will receive reminder text messages two times daily via Way to Health: Once at the start of their fast period and once during the meal that they skip during the fast period. Each week, participants and their support partner will also receive a text message noting how many days in the previous week they successfully fasted for at least 16 hours. After the 12 week intervention, these text messages will stop, but for the entire 18-week period, participants in this arm will receive the same text messages as the attention control arm: A daily text message asking if they fasted for at least 16 hours over the previous 24 hours, and a weekly text message asking for weight and blood pressure results.

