#### 4.5. End-of-Study Questionnaire Completion

At the end of the 16-week study period, patients will be alerted by the Way to Health platform to return to the website to complete an end-of-study questionnaire regarding their experience with IF.

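### The two exploratory adherence groups (≥4 versus ≤4 days per week) share the value 4, so a patient at exactly 4 belongs to both

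*Combined protocol and SAP*

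**What the plan says.** Section 5.1 lists, after the secondary outcomes, an exploratory comparison of blood pressure and weight change in "patients that were adherent to IF $\geq$ 4 days per week vs. $\leq$ 4 days per week". Section 5.3 repeats it with mixed effects regression, comparing change from baseline "in patients who reported fasting $\geq 4$ days/week versus those who reported fasting $\leq 4$ days/week". Neither sentence names the period over which a patient's days per week are counted.

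Three other statements bear on the point:

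- The primary adherence measure in section 5.1 is "captured via daily text message, over 18 weeks, expressed in days per week"; a secondary measure covers 12 weeks.
- The systolic outcome in section 5.1 is "Change in systolic blood pressure from baseline to 12 weeks and 18 weeks", and weight change has the same two time points.
- Section 4.3 writes its two stratification cuts (BMI 40 kg/m², systolic pressure 160 mmHg) with one inclusive and one strict sign, so those strata do not overlap.

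**The concern.** A two-group comparison needs groups that do not overlap. Here the boundary value satisfies both definitions, and the plan has no tie rule. Someone preparing the data would have to choose a side for any patient at exactly 4, and nothing in the plan requires that choice to be made before outcomes are known. With 34 patients in all, moving even one between groups can shift a group mean.

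The unnamed adherence period leaves a second choice open. The plan has adherence over 18 weeks and over 12 weeks, and outcomes at both times. If 18-week adherence were used to group patients for the 12-week change, part of the grouping would rest on behaviour after the outcome was measured.

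**Working it through.** The plan states no figure for this comparison, so there is none to reproduce. The check has three steps.

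**1. Do the groups overlap?** Let x be days fasted per week. The set x ≥ 4 and the set x ≤ 4 meet at x = 4. This holds whatever period is used to compute x. A conversion fault in the text is unlikely: the same pair of signs stands in sections 5.1 and 5.3, and strict signs come through in sections 3.3.1, 4.3 and 5.2.

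**2. Can a patient be at exactly 4?** For its main analysis, section 5.3 counts unreported days as non-adherent. If the same rule governs the grouping, each patient has a whole number of fasted days over a fixed number of days:

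- 18 weeks: 18 × 7 = 126 days, and 72/126 × 7 = 4.0.
- 12 weeks: 12 × 7 = 84 days, and 48/84 × 7 = 4.0.

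So the boundary value is attainable over either period.

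**3. How many patients might sit there?** Inputs:

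- N = 34 (section 5.2).
- SD of days fasted per week: 1 to 1.24. Section 5.2 prints only an upper limit, < 1.24, without a full stop. The 24 may be a citation number, which would make the limit 1. The range is therefore an assumption.
- Mean m: 2 to 6 days per week. The documents give none, so this too is assumed.
- Classification by each patient's unrounded mean over all days of W weeks: assumed.

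The mean moves in steps of 1/W, so with a normal approximation

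p = Φ((4 + 0.5/W − m)/SD) − Φ((4 − 0.5/W − m)/SD).

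The expected number is 34p, and the chance of at least one such patient is 1 − (1 − p)^34. For W = 18, m = 4 and SD = 1: p = Φ(0.0278) − Φ(−0.0278) = 0.0222, 34p = 0.75, and the chance of at least one is 53%.

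| W (weeks) | m | p, SD 1 | p, SD 1.24 | Expected of 34, SD 1 | Expected of 34, SD 1.24 |
|---|---|---|---|---|---|
| 18 | 4 | 0.0222 | 0.0179 | 0.75 | 0.61 |
| 18 | 3 or 5 | 0.0134 | 0.0129 | 0.46 | 0.44 |
| 18 | 2 or 6 | 0.0030 | 0.0049 | 0.10 | 0.17 |
| 12 | 4 | 0.0332 | 0.0268 | 1.13 | 0.91 |
| 12 | 3 or 5 | 0.0202 | 0.0194 | 0.69 | 0.66 |
| 12 | 2 or 6 | 0.0045 | 0.0073 | 0.15 | 0.25 |

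Across the table, the chance of at least one patient at exactly 4 is 10% to 53% over 18 weeks and 14% to 68% over 12 weeks.

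These ranges are not bounds. With SD 0.5 over 18 weeks, the expected number is about 1.5 at mean 4 and below 0.001 at mean 6. The normal curve is also not cut off at 7 days: at mean 6 it places 16% (SD 1) to 21% (SD 1.24) of its mass above 7, which cannot occur. The figures give an order of magnitude only.

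**The case against.** The strongest reply is that this is a one-sign slip in an exploratory, non-randomised comparison whose intent, to split at 4 days per week, is plain. On the figures above, the chance that nobody sits at exactly 4 over 18 weeks is 47% to 90%. That stands, and it is why the point is minor. It does not remove the point, because the text does not settle which side holds 4. Section 5.1 attaches the word adherent to the ≥4 group, which hints at ≥4 versus <4, but the same sentence also writes ≤4.

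A second reply is that neither sentence speaks of an average over a period. That is also fair. The overlap exists under any reading, but the counts in the table belong to the mean-over-all-days reading. If each week were classified separately, roughly 21% to 31% of weeks would equal 4 of 7 days (at an assumed mean of 3 to 5). The plan does not say that it does this.

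A third is that section 6.6.1 keeps the arms under code letters until analysis is complete. This limits placement driven by arm, but not placement driven by blood pressure or weight.

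Two stronger readings are tempting and not supported. A reader might infer that patients at 4 will be counted twice; in a two-group model each patient would normally be coded once, so arbitrary placement is the likelier result. A reader might also infer that the plan classifies patients on 18-week adherence for the 12-week outcome. It states no such rule, and matching each outcome to its own adherence period is equally natural. The period is unstated, not wrongly chosen.

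**Conclusion.** The definition is wrong as written: both signs include 4, in both sections, and no rule places a patient at that value. The severity is minor. Only the exploratory comparison is affected, and no sample size, power or alpha figure changes. Under the stated assumptions about 0.1 to 0.8 of 34 patients would be at exactly 4 over 18 weeks, with more near mean 4 if the SD is smaller. The overlap itself needs none of those assumptions.

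A reader might also tie this point to the length of follow-up. Section 4.4.1 on the control arm ("For the next 16 weeks, they will receive a daily text message") and section 4.5 ("At the end of the 16-week study period") give 16 weeks. Section 4.4.1 on the commitment device ("for the entire 18-week period, participants in this arm will receive the same text messages as the attention control arm") and section 5.1 give 18, as does section 3.1, where after a 12-week intervention "there will be a 6-week follow-up period". That conflict is real and the passages must be reconciled, but it concerns the primary outcome window. It neither causes the overlap nor has to be settled before the signs are corrected, so it should be handled as a separate issue.

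**What to change.** Before the data are seen:

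1. Make one inequality strict in both section 5.1 and section 5.3, for example ≥4 versus <4 days per week. Either sign can be changed, provided both sections agree.
2. Add a sentence naming the adherence period used for grouping, such that adherence after week 12 does not classify patients for the 12-week change.
3. Optionally, adjust this non-randomised comparison for arm and for the baseline value, which is already collected.

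The first two steps cost one character in each section and one sentence. The third adds two covariates to an exploratory model. None needs new data or a change to the sample size.
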